4.1.1.2.1 Resumption of Dose Escalation

If dose escalation is halted due to excessive DLTs or other stopping rules for safety being met ([Section 9.1](#)), dose escalation may resume if a review by the DMC of all cumulative data identifies a possible mitigating intervention(s) (e.g., corticosteroid pre-medication for injection site reaction). In such an instance, dose escalation may resume, beginning at the same dose level at which escalation ceased, implementing the proposed intervention and following the dose escalation guidelines above. If successful, any subsequent dose levels must incorporate the new intervention.

4.1.1.3 Stopping Rules for Safety (Phase 1b/2)

Please refer to [Section 9.1](#) for detailed information on stopping rules for safety.

4.1.2 Phase 2

Phase 2 is an open-label, single dose level study to evaluate the efficacy and safety of KZR-616 administered weekly in 20 patients with active proliferative LN.

Patients must be on standard therapy including at least one immunosuppressive agent.

KZR-616 at a dose level of 60 mg (including a step-up from an initial week 1 dose of 30 mg), will be administered as a SC injection weekly for 24 weeks. Safety assessments will continue for up to 12 weeks following the last dose of KZR-616.

4.2 Estimated Study Duration

For patients in the Phase 1b, screening will last approximately 4 weeks, treatment will last approximately 12 weeks (13 doses over 12 weeks and 1 day) and follow-up will last 12 weeks for a total of approximately 28 weeks of participation.

For patients in the Phase 2 portion of the study, screening will last up to 5 weeks, treatment duration is 24 weeks (24 doses over 24 weeks), and follow-up will last 12 weeks for a total of up to 41 weeks of participation.

4.3 Minimizing Bias

KZR-616-002 is an open-label study.

5 PATIENT SELECTION

5.1 Number of Planned Patients

Approximately 68 patients total, including up to 48 in Phase 1b escalating cohorts.

For Phase 2, the planned number of patients is 20. Any patient in the Phase 2 who withdraws/is withdrawn from the study for any reason prior to Week 14 can be replaced.

5.1.1 Patient Screening

Study participation begins once written informed consent is obtained (see [Section 12.3](#) for details).

Once informed consent is obtained, a sequential patient identification number will be assigned by the site, and the screening evaluations may begin to assess study eligibility (inclusion/exclusion) criteria. The patient identification number will be used to identify the patient during the screening process and throughout study participation, if applicable.

Screening assessments (see the Schedule of Assessments, [Section 14.1](#), Appendix A, and [Section 14.2](#), Appendix B, for Phase 1b and Phase 2, respectively) for this study should be performed between Day -28 and Day -1. The screening period can be extended to 35 days upon sponsor approval for Phase 1b and without sponsor approval for Phase 2. Patients who fail screening or do not meet inclusion/exclusion criteria may be re-screened one time.

5.2 Inclusion and Exclusion Criteria

5.2.1 Inclusion Phase 1b

1. Male or female patients aged 18 to 75 years (inclusive)
2. Body mass index (BMI) of 18 to 40 kg/m²
3. Fulfills the 2012 SLICC classification criteria for SLE
4. Have at least one of the following at screening per central lab:
 - a) Positive ANA test (1:80 or higher); or
 - b) Anti-dsDNA antibodies elevated to above normal (i.e., positive results); or
 - c) Anti-Smith antibody elevated to above normal (i.e., positive results)
5. Active SLE as indicated by a SLEDAI-2K total score ≥ 4 at screening
6. Must have received 1 or more of the following therapies for SLE, each administered at or higher than the minimum dose indicated for at least 12 weeks (unless discontinued or dose adjusted for documented drug-related toxicity or size/weight):
 - a) Hydroxychloroquine 200 mg orally daily in combination with prednisone 10 mg daily or equivalent
 - b) MMF orally 1 g/day or MPA orally 720 mg/day
 - c) Methotrexate orally or SC 15 mg/wk., or leflunomide orally 10 mg/day

-
- d) AZA 100 mg/day or 6-mercaptopurine 50 mg/day (50 or 25 mg/day, respectively, permitted in cases of documented thiopurine methyltransferase [TPMT] polymorphism) orally
 - e) Cyclosporine or tacrolimus at doses documented to maintain at least 100 or 5 ng/mL during the required duration, respectively
 - f) Cyclophosphamide 500 mg IV every 2 weeks or 500 mg/m² IV once monthly
 - g) Belimumab 10 mg/kg IV every 2 weeks for 3 doses, followed by 10 mg/kg every 4 weeks; or 200 mg SC weekly
 - h) Rituximab 1 g IV (may be given as 500 mg twice)
7. Acceptable screening laboratory values of concern, including:
- a) Adequate hematologic criteria:
 - Absolute neutrophil count $\geq 1.5 \times 10^9/L$ ($\geq 1 \times 10^9/L$ if neutropenia is attributable to lupus disease activity)
 - White blood cells $\geq 2.0 \times 10^9/L$ ($\geq 1.5 \times 10^9/L$ if leukopenia is attributable to lupus disease activity)
 - Hemoglobin (Hgb) ≥ 9 g/dL (≥ 8 g/dL if anemia is attributable to lupus disease activity)
 - Platelet count $\geq 100 \times 10^9/L$ ($\geq 25 \times 10^9/L$ if thrombocytopenia is attributable to lupus disease activity)
 - b) Adequate hepatic function:
 - Total bilirubin $\leq 1.5 \times$ upper limit of normal (ULN) ($3 \times$ ULN for patients with documented Gilbert's syndrome)
 - Aspartate aminotransferase (AST) $\leq 2.5 \times$ ULN
 - Alanine aminotransferase (ALT) $\leq 2.5 \times$ ULN
 - c) eGFR ≥ 40 mL/min/1.73 m² (estimated based on Chronic Kidney Disease Epidemiology Collaboration [CKD-EPI] formula)
 - d) Immunoglobulin G (IgG) ≥ 500 mg/dL
8. If taking the following SLE therapies:
- a) Oral corticosteroids (up to 20 mg/day prednisone or equivalent): must be on a stable dosage regimen of oral corticosteroid at least 4 weeks prior to screening and maintain stable dosage until randomization
 - b) Hydroxychloroquine (≤ 400 mg/day) or chloroquine (≤ 500 mg/day) orally or other antimalarials: must be started or stopped at least 12 weeks prior to screening, with stable dosage regimen for at least 4 weeks prior to screening
 - c) Immunosuppressive agents: must be started or stopped at least 12 weeks prior to screening, with stable dosage regimen, including route of administration, for at least 4 weeks prior to screening:
 - MMF (≤ 3 g/day) or MPA (≤ 2.16 g/day) orally
 - AZA (≤ 200 mg/day) orally
 - Methotrexate (≤ 25 mg/week) orally, SC, or intramuscularly (patients must be on concomitant folic or folinic acid supplementation if using methotrexate)
 - Leflunomide (≤ 20 mg/day) orally
-

-
9. Women of childbearing potential must have a negative serum beta-human chorionic gonadotropin (hCG) pregnancy test at screening and a negative urine pregnancy test prior to the first dose and must agree to use a highly effective method of birth control from signing the informed consent form (ICF) until their completion of the study (or 30 days following the last dose of study drug in case of early withdrawal). Hormonal contraception may not be effective in women on concomitant MMF/MPA; women on MMF/MPA using hormonal contraception must agree to use a highly effective non-hormonal method of contraception. Abstinence is not an acceptable method of birth control for this study. Women of nonchildbearing potential must be postmenopausal (no menses for at least 2 years before the screening visit), permanently sterilized (e.g., bilateral tubal occlusion, hysterectomy, bilateral salpingectomy), or congenitally sterile.
 10. Male patients must use an effective contraception method (e.g., condom with spermicide) from signing the ICF until their completion of the study (or 12 weeks following the last dose of study drug in case of early withdrawal) or be congenitally or surgically sterile (e.g., vasectomy with documented confirmation of post-surgical aspermia)
 11. Willing and able to provide written informed consent prior to any study-related procedures and to comply with all study requirements.

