SC administration of KZR-616 resulted in consistent, dose-proportional PK. At all dose levels tested, KZR-616 was rapidly absorbed and cleared with no accumulation following weekly repeat doses. Drug levels were below limit of quantitation by 24 hours post-dose. The pharmacology was consistent across subjects with low inter-subject variability in both exposure and target inhibition, regardless of concomitant treatment with or without corticosteroids and antihistamines. Though KZR-616 is a weak time-dependent inhibitor of

CYP3A4 and a substrate of P-glycoprotein (P-gp), the rapid clearance and extrahepatic metabolism of KZR-616 by epoxide hydrolases strongly suggest that there is minimal risk for a DDI.

Across doses of 7.5 – 75 mg, SC administration of KZR-616 resulted in selective and dose-dependent inhibition of peripheral blood mononuclear cell (PBMC) CT-L activity (predominantly immunoproteasome), with doses of ≥ 30 mg resulting in mean inhibition of PBMC CT-L activity $>80\%$ and mean inhibition of whole blood CT-L activity (predominantly constitutive proteasome) $\leq 36\%$. Data further showed that despite incomplete recovery of immunoproteasome activity on Day 7 (6 days after dosing), there was not an accumulation of proteasome inhibition. From a PK and pharmacodynamic (PD) perspective, weekly SC administration of KZR-616 appeared equivalent to serial episodic dosing.

Following a full safety assessment from multiple cohorts of subjects receiving weekly administration, KZR-616 appears to have an adequate safety profile for use in patients with SLE and LN. For further information, please see the KZR-616 Investigator's Brochure.

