 - b) History of severe and/or disseminated viral infections, and/or opportunistic infections
 - c) Known seropositivity for or active infection by human immunodeficiency virus (HIV)
 - d) Active, chronic, or resolved hepatitis B or hepatitis C infection (see [Section 8.2.6.6](#))
 - e) History of progressive multifocal leukoencephalopathy
 - f) Active or latent tuberculosis (TB), as suggested by chest x-ray within the 12 weeks prior to screening and/or QuantiFERON[®]-TB Gold at screening per [Section 8.2.6.6](#)
 - Patients with a history of latent TB with documented completed treatment per Centers for Disease Control and Prevention guidelines are allowed
 - A chest x-ray must be performed during screening if one has not been done within 12 weeks prior to the screening visit
 - g) Receipt of a live-attenuated vaccine within 12 weeks of first day of study treatment (Week 1, Day 1)
 - h) Primary immunodeficiency (unless otherwise considered, in the opinion of the investigator and medical monitor, to confer a clinically insignificant infection risk, such as deficiency in immunoglobulin A (IgA), C1q, C2, or C4 without a history of recurrent infections [3 or more infections in 1 year requiring antimicrobial therapy])
6. History of any concurrent illness, including drug induced SLE, that has required treatment with oral or parenteral corticosteroids for more than a total of 2 weeks within the last 24 weeks prior to signing the ICF
-

-
7. Clinical evidence of significant unstable or uncontrolled acute or chronic diseases (e.g., cardiac [including congestive heart failure, hypertension, angina, or history of myocardial infarction], pulmonary [including chronic obstructive pulmonary disease, asthma requiring corticosteroid therapy, pulmonary hypertension, or pulmonary fibrosis], hematologic, gastrointestinal, hepatic, renal, neurological, or infectious diseases) that, in the opinion of the investigator or sponsor, could confound the results of the study, put the patient at undue risk, or interfere with protocol adherence
 8. History of cancer, except for in situ cancer that has been completely excised or has been curatively treated with no sign of disease for > 5 years
 9. Major surgery within 4 weeks before signing the ICF or major surgery planned during the study period

5.2.3 Inclusion Phase 2

1. Male or female patients aged 18 to 75 years (inclusive)
 2. BMI of ≥ 18 kg/m²
 3. Fulfills the 2012 SLICC classification criteria for SLE

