 - A chest x-ray must be performed during screening if one has not been done within 12 weeks prior to the screening visit
 - c) Receipt of a live-attenuated vaccine within 12 weeks of Baseline (Week 1, Day 1)
 - d) Primary immunodeficiency (unless otherwise considered, in the opinion of the investigator and medical monitor, to confer a clinically insignificant infection risk, such as deficiency in IgA, C1q, C2, or C4 without a history of recurrent infections [3 or more infections in 1 year requiring antimicrobial therapy])
 - e) Primary hematopoietic cell or solid organ transplant
 7. Clinical evidence of significant unstable or uncontrolled acute or chronic diseases (e.g., cardiac [including congestive heart failure, hypertension, angina, or history of myocardial infarction], pulmonary [including chronic obstructive pulmonary disease, asthma requiring corticosteroid therapy, pulmonary hypertension, or pulmonary fibrosis], hematologic, gastrointestinal, hepatic, renal, neurological, or infectious diseases) that, in the opinion of the investigator or sponsor, could confound the results of the study, put the patient at undue risk, or interfere with protocol adherence
 8. QT interval with Fridericia's correction (QTcF) or Bazett's correction (QTcB) > 480 msec on ECG
 9. Major surgery within 12 weeks before signing the ICF or major surgery planned during the study period
 10. Any active or suspected malignancy or history of documented malignancy within the last 5 years before Screening. Exceptions include history of appropriately excised and cured cervical carcinoma in situ or excised basal or squamous cell carcinomas of the skin
 11. Women who are pregnant or lactating
 12. Hypersensitivity to the Investigational Medicinal Products or any of its excipients.
 13. Use of investigation medical therapy or device, and/or participation in an investigational trial < 8 weeks or 5 half-lives, whichever is longer, prior to Baseline; Patients who participated in Phase 1b of KZR-616-002 are excluded from Phase 2
-

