8.2.6.10 Pregnancy Evaluation

Women of childbearing potential (WOCBP) must have a negative serum pregnancy test at the screening visit, which is confirmed to be negative by urine testing prior to the first dose of study drug at Week 1 and prior to further dosing at each study visit thereafter. WOCBP are defined as: all postpubescent female patients, unless the patient is postmenopausal (defined by amenorrhea for at least 2 years or amenorrhea for at least 1 year with confirmatory follicle stimulating hormone [FSH] level in the postmenopausal range as documented historically or measured by the central laboratory at Screening and if patient is not on supplementary hormonal therapy) or if the patient is surgically sterile (i.e., tubal ligation, hysterectomy, bilateral salpingoophorectomy).

Please refer to Inclusions 9 and 10 for both the Phase 1b and Phase 2 studies for contraception requirements.

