9.2 Early Withdrawal of Patients from Study

Patients may stop study drug for any of the following reasons:

-
- Patient request/withdraw consent due to an AE
 - Patient request/withdraw consent for any reason other than an AE
 - Patient becomes pregnant
 - Use of non-permitted concurrent therapy
 - Non-compliance with the study drug or study schedule
 - AE of \geq Grade 4
 - Lost to follow-up
 - Occurrence of AEs not compatible with the continuation of patient participation in the study, in the investigator's or sponsor's opinion, or unacceptable to the patient to continue
 - Investigator request
 - Sponsor request

For Phase 1b, patients who do not comply with the protocol or who withdraw consent may be replaced. For Phase 2, only patients who withdraw before the Week14 injection may be replaced.

Patients are free to withdraw from the study at any time without providing reason(s) for withdrawal and without prejudice to further treatment. The reason(s) for withdrawal will be documented in the eCRF. If a patient withdraws consent, all samples obtained will be retained for analysis unless the patient confirms that he or she wishes the samples to be discarded.

Patients withdrawing from the study treatment will be encouraged to complete the Early Withdrawal Visit within 7 days and return for an EOS Visit approximately 12 weeks after receipt of their last dose to complete the final evaluations according to this protocol, particularly safety evaluations. The aim is to record data in the same way as for patients who completed the study.

Reasonable efforts will be made to contact patients who are lost to follow-up. These efforts must be documented in the patient's file.

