10.3 Pregnancy Reporting

Pregnancy occurring during a clinical investigation must be reported to safety within 24 hours on a Pregnancy Monitoring Form. The outcome of a pregnancy should be followed up carefully and any abnormal outcome of the mother or the child should be reported. This also applies to pregnancies following the administration of the investigational product to the father prior to sexual intercourse. Infants should be followed for a minimum of 8 weeks and all findings should be reported to the sponsor. Study drug is to be discontinued immediately.

If the outcome of the pregnancy meets a criterion for immediate classification as an SAE—spontaneous abortion (any congenital anomaly detected in an aborted fetus is to be documented), stillbirth, neonatal death, or congenital anomaly—the investigator should repeat the procedures for expedited reporting of SAEs as outlined above.

Full details will be recorded on the withdrawal page of the eCRF, or an SAE report will be completed if the patient has completed the study.

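### Phase 1b does not exclude lactating women, although Phase 2 exclusion 11 does, and the protocol gives no reason for the difference

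*Combined protocol and SAP*

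**What the plan says.** Phase 1b inclusion 9 (Section 5.2.1, repeated in the synopsis) reads in part: "Women of childbearing potential must have a negative serum beta-human chorionic gonadotropin (hCG) pregnancy test at screening". It adds a negative urine test before the first dose and highly effective contraception. It says nothing about breastfeeding.

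The Phase 1b exclusions (Section 5.2.2 and synopsis) run to nine items. The last is "Major surgery within 4 weeks before signing the ICF or major surgery planned during the study period". None of the nine concerns lactation.

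Phase 2 exclusion 11 (Section 5.2.4 and synopsis) is "Women who are pregnant or lactating". It stands under the Phase 2 heading in both places.

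Section 8.2.6.10, which serves both phases, covers pregnancy testing and the definition of childbearing potential, then sends the reader back to the criteria: "Please refer to Inclusions 9 and 10 for both the Phase 1b and Phase 2 studies for contraception requirements".

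**The concern.** The two parts of the protocol give the same drug by the same route on the same weekly schedule. The sponsor treats lactation as a bar to entry in Phase 2 and is silent on it in Phase 1b, the dose-escalation part, which goes up to 75 mg against 60 mg in Phase 2. An hCG test and a contraception requirement screen for pregnancy. They do not identify a woman who is breastfeeding.

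The person at stake is the infant, who is not a study patient. Sentinel dosing, the dose-limiting-toxicity rules and the management of systemic reactions all protect the woman being treated.

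**Working it through.** No arithmetic applies, and the plan states no figure on this point. The check is whether any written rule makes a lactating woman ineligible for Phase 1b, or deals with her once she is dosed.

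**Entry rules**

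| Place | What it covers | Does it exclude lactation? |
|---|---|---|
| 5.2.1, inclusion 9 (Phase 1b) | Pregnancy tests, contraception | No |
| 5.2.1, inclusion 11 (Phase 1b) | Consent and compliance | No |
| 5.2.2, exclusions 1 to 9 (Phase 1b) | CNS disease, overlap disease, antiphospholipid syndrome, prior treatments, infection, other steroid-treated illness, unstable disease, cancer, surgery | No |
| Synopsis, Phase 1b lists | Same items | No |
| 5.2.4, exclusion 11 (Phase 2), and synopsis | Pregnancy and lactation | Yes, Phase 2 only |
| 8.2.6.10 (both phases) | Pregnancy testing | No |
| Appendix E | Excluded medications | No |

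The broadest Phase 1b clause is exclusion 7: "Clinical evidence of significant unstable or uncontrolled acute or chronic diseases". It applies where such disease could confound results, endanger the patient or hinder adherence. Lactation is not a disease, and the infant is not the patient, so the clause does not reach this case.

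**Rules after entry**

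- Section 7.1.1 sets the conditions for each dose: blood counts, liver tests and adverse-event grade. Lactation is not among them.
- Section 9.2 lists reasons for stopping drug. It names "Patient becomes pregnant" but not lactation. It also allows stopping at the request of the investigator or the sponsor.
- Section 9.1 lets the investigator, medical monitor, DMC or sponsor's representative stop an individual's dosing for an event they judge to contraindicate it.
- Section 10.1.1 defines an adverse event as something occurring in a study patient.
- Section 10.3 says "Infants should be followed for a minimum of 8 weeks and all findings should be reported to the sponsor", but in the setting of a pregnancy reported during the study.
- Sections 10.2.1 and 10.2.2 allow judgement-based notification of a significant hazard or of an event of serious clinical concern.

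**Result.** There is no lactation bar in Phase 1b and one in Phase 2, worded identically in the synopsis and the body. A breastfeeding woman who tests negative for hCG, agrees to contraception and meets the disease and laboratory criteria is eligible for Phase 1b as written. After entry, only clauses that depend on someone's judgement could apply to her, and none of them names an infant exposed through milk.

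**The case against.** **The lists differ in many ways.** They also differ on the BMI ceiling, the eGFR limit (40 against 30), QTc, the surgery window (4 against 12 weeks) and abstinence, so a difference alone is not an error. That is fair. What remains is that the protocol gives no reason for this one, and nothing in the change of disease population explains why a breastfed infant would need the bar in one part only.

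**Discretion may be enough.** A reader might infer that nothing in the protocol could stop treatment or prompt a report. The documents do not support that: the clauses in Sections 9.1, 9.2, 10.2.1 and 10.2.2 give real routes to both. They do not make the woman ineligible, and they work only if someone thinks to use them. Nor does the silence of Sections 9.2 and 10.3 on lactation show a fault peculiar to Phase 1b, since both sections also serve Phase 2.

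**Clearance is fast.** Section 2.4 reports from healthy volunteers that "Drug levels were below limit of quantitation by 24 hours post-dose", and Section 7.2 gives a half-life under 2 hours. This argues for limited exposure. It does not establish safety for an infant. The documents give no data on transfer into milk or infant dose, and no corresponding clearance time for the metabolite KZR-59587, whose human AUC in Table 1 is 190% to 240% of the parent's. A reader might also infer that infants would be harmed. The documents do not support that either.

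**The change may come too late.** Phase 2 is already fixed at 60 mg, and Phase 2 exclusion 13 refers to Phase 1b participants in the past tense, which suggests that dose selection is over. Yet the synopsis and Section 10.7 still describe Phase 1b as work to come. Enrolment status is not settled, and this objection stands as a condition on the fix.

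**Conclusion.** The gap is real on the text: Phase 1b admits lactating women whom Phase 2 excludes, with no stated reason. It is a minor point and a cheap improvement. Phase 1b is planned for up to 48 patients. The number who might be breastfeeding is not given and is probably small. No endpoint, sample size or analysis is affected.

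Confidence is high for the reading of the criteria. Any practical consequence rests on two assumptions: that Phase 1b is still open to enrolment, and that a breastfeeding woman would present for screening. The consent form was not available for this review and may carry a warning. Even so, the eligibility bar belongs in Section 5.2, where Phase 2 has it.

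**What to change.** If Phase 1b is still enrolling, add Phase 2 exclusion 11, "Women who are pregnant or lactating", to the Phase 1b exclusions in Section 5.2.2 and in the synopsis. The pregnancy half repeats what inclusion 9 already secures and does no harm.

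Add lactation status to the screening medical history. Section 8.2.1 does not list it at present, so sites would need the prompt.

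The cost is one line of text in two places, one screening question and at most a few extra screen failures. No test or visit is added. If Phase 1b enrolment has closed, the amendment would have no practical effect.
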